2.3.2 Potential Mechanism of Action

GCSF, an agent well known to help mobilize hematopoietic precursors from the bone marrow, has been used clinically for nearly 20 years to help repopulate peripheral cell counts in patients undergoing cancer therapy. However, a rapidly growing body of experimental and clinical evidence suggests that GCSF has the potential to be used in the treatment of autoimmune diseases. GCSF has been shown to favor the differentiation and mobilization of Treg cells, induce tolerogenic DC, and alter the balance between proinflammatory and anti-inflammatory soluble mediators both animals and in humans (Figure 3) (65-67). Specifically, GCSF can mobilize functional bone marrow CD4⁺CD25⁺FoxP3⁺ Treg cells. Preclinical models of GCSF-induced inhibition of autoimmune and allogeneic T cell responses have demonstrated the potential efficacy of GCSF in treating Crohn disease, myasthenia gravis, and T1D.

[figure not shown]

Figure 1. Effects of GCSF on immune function. The GCSF induced modulation of cytokine production, T cell polarization, and

DC functional profile is depicted schematically. GCSF can alter the balance between pro-inflammatory and anti-inflammatory soluble mediators, favor the differentiation and mobilization of Treg cells, and induce tolerogenic DC both in animals and in humans. (*Adapted from Rutella et al, J. Immunology 2005, 175: 7085–7091, (65).*)

With this extensive experience of clinical use, GCSF therapy is known to be both safe and well tolerated. The side effect profile of short course GCSF therapy is limited; with frequency and severity of toxicities being dose dependent (greater with larger doses and longer duration) and minimal in comparison to many of the agents being used in current T1D intervention studies. Specifically, the most common side effect associated with GCSF therapy is bone pain (occurring in 10-20% of patients) which occurs 2-3 days after initiation of therapy. This discomfort is generally controllable with acetaminophen. Infrequent side effects include redness at injection site, fever, headache, chest pain and dizziness (occurring in less than 10% of patients).

2.4 Combination of ATG and GCSF

2.4.1 GCSF Enhances Reversal of Diabetes Afforded by murine ATG in the NOD

To determine the efficacy of a combination of ATG and GCSF in NOD mice with 'new-onset' diabetes, female NOD mice were monitored 3 times per week for hyperglycemia (defined as a blood glucose > 240mg/dL) by tail bleed for up to 150 days as shown (Figure 2).

[figure not shown]

Figure 2. Blood glucose values were obtained for up to 150 days post-onset in NOD mice treated with (a) control (two IP injections of 500 ug rIgG), (b) GCSF (Neupogen (Amgen, Inc.) 6ug daily x 8weeks, (c) murine ATG (two IP injections of 500 ug murine ATG, or (d) murine ATG + GCSF. All received sustained release insulin for 3 weeks.

As shown (Figure 2), the administration of murine ATG alone to new-onset NOD mice resulted in durable (i.e., > 150 days post-onset) remissions from overt hyperglycemia in 33% (5/15) of treated animals, while neither control (0/16) nor GCSF monotherapy (0/14 mice) provided such reversions. However, the combination of murine ATG and GCSF

therapy resulted in a remission rate of 75%, a significantly greater rate of remission than was seen with murine ATG monotherapy (12/16; $P = 0.0000006$ versus control, $P = 0.013$ versus murine ATG).

Interestingly and very importantly, in terms of dosage in humans, GCSF improved the therapeutic capacity for diabetes reversal even when in combination with a suboptimal dose (290ug) of murine ATG. Moreover, successful treatment with murine ATG was largely limited to

values of ≤ 380 mg/dL (mean 317.2mg/dL; range 256-398mg/dL), whereas combination therapy of murine ATG and GCSF significantly increased the therapeutic ceiling to ~ 500 mg/dL (mean 401.8 mg/dL; range 264-500mg/dL). Additional studies demonstrated an improvement in IP glucose tolerance tests (IPGTT) at from the 60 to 120 day time points. This improvement in glucose control occurred in spite of the cessation of both murine ATG and GCSF therapies prior to the 60-day time point.

2.4.2 ATG + GCSF Combination Therapy Induces Immunomodulation

To address the question of whether GCSF-mediated enhancement of diabetes reversal was due to induction of immunoregulation, murine ATG and GCSF (as both mono- and combination-therapy) were administered to pre-diabetic 12-week-old female NOD mice for up to 8 weeks. Analysis of peripheral blood revealed marked leukocyte depletion in murine ATG-treated mice versus all other groups at 2 week, with movement back towards pre-treatment levels at 4 and 8 weeks post-induction. However, the addition of GCSF to murine ATG afforded a significant increase in leukocytes at 2 weeks versus murine ATG alone. In particular, GCSF increased the percentage of splenic macrophages and neutrophils. Both murine ATG as well as GCSF have been reported to induce a population of Treg *in vivo*. Predictably, all treatments utilized in these efforts herein demonstrated a reduced percentage of Treg at 2 weeks versus control animals due to either short-term depletion by murine ATG or mobilization of macrophages and neutrophils by GCSF. GCSF therapy led to an increase in Treg versus control as early as 4 weeks while combination therapy had the greatest increase in Treg versus all other treatments at 8 weeks. As indicated by the increase in Treg the immunomodulatory benefit afforded by GCSF continued through 8 weeks, despite the lack of mobilization of macrophages and neutrophils beyond 2 weeks. Thus the greatest percentage of Treg cells was observed in mice receiving combination therapy. The health of the islets at the endpoint of the pre-diabetic study was an important consideration. As such, insulinitis scoring was performed to determine the degree of lymphocytic infiltration over the 8 weeks of therapy in pre-diabetic NOD mice. Combination therapy resulted in markedly lower insulinitis intensity scores when compared with islets from control animals after 8 weeks. In addition, insulin staining revealed improved beta cell area in animals receiving combination therapy versus murine ATG monotherapy, while control animals demonstrated a decline in beta cell area over the 8 week period.

By combining these two monotherapies, however, the health of the islets was maintained relative to control as measured by insulinitis scoring and beta cell area. These results indicate that combined treatment of murine ATG with GCSF offers a highly effective means for reversal of T1D in NOD mice.

2.5 Monotherapy and Combination Therapy Clinical Trial Updates

2.5.1 GCSF Monotherapy

In August of 2008, the University of Florida T1D research group embarked on a pilot (JDRF/NIH supported) study of GCSF monotherapy, in order to firmly establish the safety of GCSF and demonstrate the potential for efficacy in mobilizing Treg in the T1D population. The study used a 2:1 drug: placebo randomization scheme and AUC C-peptide as the primary efficacy outcome measure. Twenty-one study participants completed a 12 week course of the study drug (GCSF 6mg sq q 2 weeks versus placebo). Analysis of the 12 month follow-up data did not demonstrate any significant preservation of C-peptide in treated subjects. Drug was well tolerated with the most frequent complaints being bone pain or headache treatable with ibuprofen or acetaminophen. In addition, there were no issues with splenomegaly or concerning elevation of the absolute neutrophil count.

2.5.2 ATG Monotherapy

In late 2006, the ITN approved ATG monotherapy in new-onset T1D at a limited number of sites; the START trial (Study of Thymoglobulin to Arrest Type 1 Diabetes). After safety and tolerability of the drug was demonstrated, the age group was lowered to 12 years in the Fall of 2009 and the study was fully enrolled. The primary endpoint analysis was completed in 2012 and did not reveal any benefit for ATG monotherapy (at 6.5mg/kg) in preserving beta cell function in new onset subjects (41b).

2.5.3 ATG +GCSF

A phase IIa study of ATG (2.5mg/kg) and GCSF (6mg q 2 weeks x 6 doses) utilizing a 2:1 randomization scheme (Drug: placebo) is currently underway in “established” (diagnosed for 4 months to 2 years) T1D patients (Figure 3). The study is fully enrolled (n=25) and data from all 25 subjects at the 3, 6, and 9, and 12 month study visits demonstrate ***increased*** AUC C-peptide amongst the treated subjects in comparison to those who have received placebo.

[figure not shown]

Figure 3. AUC C-peptide in Treated (ATG/GCSF) and Placebo Subjects with Established T1D. P=0.05 at 12 months

The dose of ATG for the pilot study and the current protocol was chosen based on a combination of the demonstrated safety and efficacy in treating human autoimmune and alloimmune diseases in adults and children, and the suggestion from our animal data indicating that lower dose ATG could be used successfully when utilized in combination with GCSF. Several autoimmune diseases (e.g., SLE, RA, Wegner's Granulomatosis, Systemic Sclerosis, and T1D) have been treated with some success with ATG based protocols utilizing doses from 2.5mg/kg to in excess of 10 mg/kg (68). In addition, induction therapy for kidney transplantation using low doses of ATG (2.5-5mg/kg) has demonstrated efficacy in protecting the graft and reducing acute rejection in both children and adults (69, 70).

In the ITN START study, subjects received ATG at a total dose of 6.5 mg/kg (0.5 mg/kg Day 1, then 2 mg/kg for next 3 doses). This dose has been effective and well tolerated in bone marrow and solid organ transplantation, and is well below the dose of 20 mg/kg that has been used for some transplantation protocols. Based on the observed efficacy in the mouse with combined low-dose ATG and GCSF therapy, the dose of ATG was reduced, albeit somewhat empirically, to 2.5 mg/kg with the hopes of minimizing side effects while still providing for efficacy in preserving beta cell function.

The dose and duration of GCSF was chosen on the basis of its safety as demonstrated to date in the T1D study completed at the University of Florida, and on the basis of other 12-week GCSF studies that have demonstrated potential for benefit in autoimmune disease (71).

Summary pre-clinical and preliminary clinical data:

Preclinical data demonstrate that combination therapy of ATG and GCSF has multiple beneficial mechanistic actions (e.g., increased Treg frequency, reduced islet inflammation, improved beta cell area, etc.) and dramatically extends the range of beta cell dysfunction allowable for effective and durable disease remission. Pilot clinical trial data have demonstrated efficacy in preserving C-peptide and have confirmed an acceptable safety profile. Collectively, these studies provide strong support for the performance of phase II human T1D trials with this combination of agents.

3 STUDY DESIGN

3.1 Overview

Summary of Inclusion and Exclusion Criteria

3.1.1 Inclusion Criteria

Potential participants must **meet all** of the following inclusion criteria:

1. Must be ≥ 12 years < 46
2. Must have a diagnosis of T1D for less than 100 days at randomization
3. Willing to provide Informed Consent or have a parent or legal guardian provide informed consent if the subject is <18 years of age
4. Positive for at least one islet cell autoantibody; GAD65A, mIAA, if obtained within 10 days of the onset of insulin therapy, IA-2A, ICA, or ZnT8A

5. Must have stimulated C-peptide levels ≥ 0.2 pmol/ml measured during a mixed meal tolerance test (MMTT) conducted at least 21 days from diagnosis of diabetes.
Randomization should occur within one month (37 days) of the MMTT. However, with prior approval by TrialNet, this window may be extended to allow randomization within 8 weeks (56 days).
6. Subjects who are EBV seronegative at screening must be EBV PCR negative within 30 days of randomization and may not have had signs or symptoms of an EBV compatible illness lasting longer than 7 days within 30 days of randomization
7. Be at least 6 weeks from last live immunization
8. Participants are required to receive killed influenza vaccination at least 2 weeks prior to randomization when vaccine for the current or upcoming flu season is available
9. Be willing to forgo vaccines during the treatment period and for 3 months following last dose of study drug
10. Be willing to comply with intensive diabetes management

3.1.2 Exclusion Criteria

Potential participants must **not** meet any of the following exclusion criteria:

1. Be immunodeficient or have clinically significant chronic lymphopenia: (Leukopenia ($< 3,000$ leukocytes / μ L), neutropenia ($< 1,500$ neutrophils/ μ L), lymphopenia (< 800 lymphocytes/ μ L), or thrombocytopenia ($< 100,000$ platelets/ μ L).
2. Have active signs or symptoms of acute infection at the time of randomization
3. Have evidence of prior or current tuberculosis infection as assessed by PPD, interferon gamma release assay or by history
4. Be currently pregnant or lactating, or anticipate getting pregnant within the two year study period
5. Require use of other immunosuppressive agents including chronic use of systemic steroids
6. Have evidence of current or past HIV, Hepatitis B or Hepatitis C infection
7. Have any complicating medical issues or abnormal clinical laboratory results that may interfere with study conduct, or cause increased risk to include pre-existing cardiac disease, COPD, sickle cell disease, neurological, or blood count abnormalities
8. Have a history of malignancies other than skin
9. Evidence of liver dysfunction with AST or ALT greater than 3 times the upper limits of normal
10. Evidence of renal dysfunction with creatinine greater than 1.5 times the upper limit of normal
11. Vaccination with a live virus within the last 6 weeks

12. Current or ongoing use of non-insulin pharmaceuticals that affect glycemic control within prior 7 days of screening
13. Active participation in another T1D treatment study in the previous 30 days
14. Prior treatment with abatacept or anti-cd3
15. Known allergy to GCSF or ATG
16. Prior treatment with ATG or known allergy to rabbit derived products
17. Any condition that in the investigator's opinion may adversely affect study participation or may compromise the study results

3.2 Description of Treatment Groups

This protocol will enroll at least 84 participants who will be randomly assigned to the following groups:

- 28 participants will be assigned to receive ATG + GCSF
- 28 participants will be assigned to receive ATG + Placebo
- 28 participants will be assigned to receive Placebo + Placebo

3.3 Treatment Assignment and Double Masking

After participants sign the consent form they will be randomized to one of the three arms. The randomization method will be stratified by TrialNet study site. The participants will not be informed regarding the intervention assignment until the end of the study. The investigator and clinic personnel will also be masked as to study assignment. Laboratories performing assays for this protocol will be masked as to the identity of biological material to be studied.

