8.1 Primary Outcome and Analyses

The primary outcome of each participant is the area under the stimulated C-peptide curve (Y_{AUC}) over the first 2 hours of a mixed meal glucose tolerance test conducted at the one-year visit. The Y_{AUC} is computed using the trapezoidal rule which translates into a weighted sum of the timed C-peptide values over the 120 minute MMTT. The more appealing quantity is the AUC mean which is $\frac{Y_{AUC}}{120}$ in nmol/L and will be denoted as Y_{Cp} .

Let $Y_{Cp}^{ATG/GCSF}$, Y_{Cp}^{ATG} , and $Y_{Cp}^{Control}$ represent the C-peptide AUC mean for study patients receiving both ATG and GCSF, receiving ATG alone, and those receiving placebo, respectively. Likewise, let $\mu_{Cp}^{ATG/GCSF}$, μ_{Cp}^{ATG} , and $\mu_{Cp}^{Control}$ represent the population mean of C-Peptide for these groups at one year, respectively.

The primary statistical hypotheses to be assessed in the study are:

$$H_0: \mu_{Cp}^{ATG/GCSF} = \mu_{Cp}^{Control} \text{ versus } H_a: \mu_{Cp}^{ATG/GCSF} > \mu_{Cp}^{Control}$$

$$H_0: \mu_{Cp}^{ATG} = \mu_{Cp}^{Control} \text{ versus } H_a: \mu_{Cp}^{ATG} > \mu_{Cp}^{Control}$$

The primary analysis will be conducted on a transformed scale using the function $\log(Y_{Cp} + 1)$. This provides better normal distributional behavior by the test statistic. The comparison between any two treatment arms will be based on a Wald test of treatment effect in an ANCOVA model adjusting for gender, baseline age, and baseline $\log(Y_{Cp} + 1)$.

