8.4 Sample Size and Power Calculations

The primary analysis will compare the difference in C-Peptide between experimental and placebo treatment groups at 12 months using $\log(Y_{Cp} + 1)$ transformation and ANCOVA model adjusting for gender, baseline age and the baseline value of $\log(Y_{Cp} + 1)$. Estimates of the mean and standard deviation of $\log(Y_{Cp} + 1)$ (expressed algebraically as: $\hat{\mu}_{\log(Y_{Cp} + 1)}$ and $\hat{\sigma}_{\log(Y_{Cp} + 1)}$) in the placebo group were derived from the last four TrialNet studies of early onset disease. The 90% confidence bound estimates were used to provide good confidence that this trial's study population characteristics fall within these limits to assure the advertised statistical power; the estimates are $\hat{\mu}_{\log(Y_{Cp} + 1)} = 0.360$ and $\hat{\sigma}_{\log(Y_{Cp} + 1)|X} = 0.167$ (i.e., the residual mean squared error regressing on gender, baseline age and C-peptide). The geometric-like mean of Y_{Cp} for the placebo group is $\exp(0.36) - 1 = 0.433$ nmol/L.

Using standard equations for the comparison of two means and a 1:1:1 allocation, a sample size of 78 participants (26 per group) with complete data would provide power of 85% to detect a 50% increase in the geometric-like mean in either experimental treatment group (compared to the control) using the Wald test (from the adjusted linear model) at the 0.025 level (one-sided). Thus the overall Type I error for both tests is approximately 0.05.

Assuming that 10% of the participants will have missing data (one-year MMTT was not done or subject withdrew prior to the one-year assessment), the sample size goal for this study will be set at 84 participants (28 per group).

The study will be closed to additional participants when the total number then randomized plus a fraction of those in screening (i.e., screening for eligibility) is expected to provide the proper number of eligible participants. Participants who had already conducted the initial screening visit at that time will be allowed to complete screening and be randomized if both consenting and eligible.

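### Randomisation is stratified by site but the primary ANCOVA omits site: the test stays valid, but may be mildly conservative and lose a little precision if sites differ

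*Protocol*

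**What the plan says.** Section 3.3 of the protocol states "The randomization method will be stratified by TrialNet study site" and names no other factor. Section 8.1 bases each comparison on "a Wald test of treatment effect in an ANCOVA model adjusting for gender, baseline age, and baseline" log-transformed C-peptide. Section 8.4 uses the same three covariates for the power calculation, section 8.6 runs the interim efficacy and futility tests on that model, and section 8.2 carries it into the secondary C-peptide analyses. Site appears in none of these, and no reason is given. The number of sites, the block size and the between-site variance are not stated.

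**The concern.** Stratifying by site balances the arms within each site, so differences between sites largely cancel out of the treatment contrast. An analysis without site does not know this. It leaves between-site variation in the residual, and its standard error then describes a noisier comparison than the one actually randomised. If sites differ in one-year C-peptide after allowing for gender, age and baseline, the reported standard error is too large and the test rejects too seldom.

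At stake is a possible modest gain in power that the design has already paid for, in a trial planned on 26 evaluable participants per arm. Because the covariate list is fixed in the protocol, this concerns what the document states and is not a detail left for later.

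**Working it through.** **1. Reproduce the plan's sample size (section 8.4).** Inputs: placebo mean 0.360 on the log(Y+1) scale, which is "0.36) - 1 = 0.433$ nmol/L"; residual SD 0.167, conditional on gender, age and baseline C-peptide but not site; design effect "to detect a 50% increase in the geometric-like mean in either experimental treatment group"; test "at the 0.025 level (one-sided").

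- Effect: δ = log(1 + 1.5 × 0.4333) − 0.360 = 0.1408.
- n per group = 2(1.960 + 1.036)² × (0.167/0.1408)² = 25.3, rounded up to 26.
- Power at 26 = Φ(0.1408/(0.167 × √(2/26)) − 1.96) = 86.0%.

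The plan says "a sample size of 78 participants (26 per group) with complete data would provide power of 85" per cent. It reproduces with a site-free SD, so the stated power does not rely on site adjustment.

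**2. Upper bound on what site could return.** Let ICC be the share of residual variance due to site (assumed; not in the protocol). If all of it were recovered at no cost, power = Φ(0.1408/(0.167 × √(1 − ICC) × √(2/26)) − 1.96):

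| ICC | Power | Gain over 86.0% |
|---|---|---|
| 0.02 | 86.7% | 0.7 |
| 0.05 | 87.7% | 1.7 |
| 0.10 | 89.3% | 3.3 |

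These are ceilings, because a real model has to estimate the site effects.

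**3. Simulation of realistic site adjustment.** Assumed settings: 78 participants in three arms, permuted blocks of 3 within site, unequal site sizes, total residual SD 0.167, 8, 14 or 20 sites. Power without site → with site, in per cent:

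| ICC | Sites | Fixed site effects | Random site intercept (REML) |
|---|---|---|---|
| 0 | 8 | 82.4 → 81.8 | 82.4 → 83.0 |
| 0 | 14 | 83.2 → 81.3 | 82.7 → 83.1 |
| 0 | 20 | 84.3 → 79.9 | 84.3 → 84.9 |
| 0.05 | 8 | 84.4 → 85.0 | 83.5 → 84.7 |
| 0.05 | 14 | 85.6 → 84.2 | 83.8 → 85.1 |
| 0.05 | 20 | 84.2 → 82.4 | 85.1 → 86.4 |
| 0.10 | 8 | 85.2 → 86.7 | 84.7 → 86.9 |
| 0.10 | 14 | 85.0 → 85.5 | 84.4 → 86.2 |
| 0.10 | 20 | 84.6 → 84.2 | 84.7 → 87.2 |

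The two columns come from separate runs, so only the change within a cell is meaningful (2,500 runs per cell for fixed effects, 2,000 for the random intercept; Monte Carlo error on a single power figure about 0.7 to 0.8 points). A further independent simulation of the random intercept (3,000 runs) gave gains of 0.6 to 0.7 points at ICC 0.02, 1.0 to 1.4 at 0.05 and 1.8 to 2.3 at 0.10.

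- Random intercept: gain of about 1 to 2.5 points at ICC 0.05 to 0.10, and no loss in any cell. The 0.4 to 0.6 points at ICC 0 cannot be recovered site variance. They are within simulation noise or reflect slight small-sample liberality: type I error with the random intercept ran from 0.022 to 0.031, averaging about 0.027.
- Fixed effects: the change reverses sign, with a loss of 4.4 points (84.3 − 79.9) at 20 sites and ICC 0.

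**4. Type I error without site.** One-sided rates were about 0.014 to 0.031 against 0.025. The highest value, 0.031, came at ICC 0 with 8 sites, where the fixed-site model gave the same rate, so it is simulation noise. At ICC 0.20 the rates were 0.014 to 0.020: conservative, as the theory predicts.

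**The case against.** The strongest reply is that nothing in the plan is wrong. Sections 8.1 and 8.4 agree on the model and the sample size reproduces. The SD of 0.167 comes from earlier studies regressed on the same three covariates, so any site variation in those data is already inside it. Section 8.5 also re-estimates the residual error at mid-trial. All of this stands. A reader might infer that the standard errors are invalid, that type I error is inflated or that the 85% power is overstated. The documents support none of these: the only possible error is in the conservative direction.

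Nor do the documents show that precision is actually lost. Baseline age is already in the model. Section 4.4 sets a common HbA1c goal with central review and leaves primary responsibility for diabetes care with the treating or referring provider. Sections 9.2 and 9.3 allow participation at more than one site and follow-up at non-treating sites, so the stratification site need not be where the one-year meal test is done. A material site effect is possible but undocumented.

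Leaving site out can be a sensible choice when sites are many and small, and the fixed-effects results show why. That argument does not carry over to a random intercept, which lost no power in the simulations. The unseen analysis plan may give a reason or add a site sensitivity analysis, but the primary model is fixed in the protocol.

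**Conclusion.** The point holds in a conditional form and is minor. The analysis omits the only named randomisation stratum. If site is prognostic beyond gender, age and baseline C-peptide, the standard error is somewhat too large and the test mildly conservative. Validity and the stated 85% power are unaffected.

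The likely gain from a random intercept is about 1 to 2.5 points of power if site accounts for 5% to 10% of the residual variance, and about nothing if sites do not differ. The ceilings of 1.7 and 3.3 points should not be read as the expected gain, since they assume full recovery of the site variance. All of this rests on assumed site shares, 8 to 20 sites and blocks of 3.

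**What to change.** Prespecify site as a random intercept in the primary ANCOVA and in the interim efficacy and futility tests. Use a small-sample degrees-of-freedom method such as Kenward-Roger, and set a rule in advance for pooling very small sites. Keep the planned three-covariate ANCOVA as a sensitivity analysis. Do not use fixed site effects.

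The cost is some extra specification. Sections 8.4 to 8.7 tie the selection rule, the sample size re-estimation and the stopping boundaries to the present linear model, so they should say which model and which residual variance they use. The site variance may also be estimated as zero: in simulation this happened in about 35% of runs at ICC 0.05 and 50% at ICC 0.02. The result then reverts to the planned ANCOVA. If the sponsor prefers to leave the primary model unchanged, the minimum is to state why site is omitted and to prespecify the random-intercept model as the sensitivity analysis.
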